5.1.2. Secondary Endpoints

Secondary endpoints are as follows:

- The proportion failed by 12 weeks is denoted as the progression rate survival and is derived based on the sum of progression events, death events, and subjects who discontinue the trial due to an Adverse event (AE).
- The ORR, defined as the rate of CR plus the rate of PR at 12 weeks following the start of Ad-RTS-hIL-12 immunotherapy
- The DCR, defined as the proportion of subjects who have a CR, PR, or stable disease at 12 weeks following the start of one cycle of Ad-RTS-hIL-12 immunotherapy
- The number of subjects whose baseline tumor status (stable disease or PR) improves to PR or better at 12 weeks following the start of Ad-RTS-hIL-12 immunotherapy
- The radiographic responses by irRC with conventional reporting by RECIST
- Tumor and serum immune biomarkers

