For subjects with HER2- disease, the Ad-RTS-hIL-12 immunotherapy is intended to be given as a chemotherapy holiday, for example, to avoid intolerable or undesirable toxicity of the standard therapy. Ad-RTS-hIL-12 immunotherapy must be started within 4 weeks of stopping the prestudy standard chemotherapy.

Subjects with HER2+ disease will receive Ad-RTS-hIL-12 immunotherapy in conjunction with first-, second-, or third-line anti-HER2 antibody therapy, i.e., subjects may continue anti-HER2-directed antibody therapy during the study period. Anti-HER2 antibody therapy will be administered according to the manufacturer's recommendations. Subjects with HER2+ breast cancer who continue the anti-HER2 antibody therapy need to recover from any anti-HER2-related AE/serious adverse event (SAE), i.e., the event must have resolved to Grade 1 or baseline, before starting Ad-RTS-hIL-12 immunotherapy.

The Ad-RTS-hIL-12 immunotherapy cycle is a 21-day cycle comprised of investigational product administration on Days 1 through 7 followed by rest on Days 8 through 21. On Day 1, enrolled subjects will receive the first dose of veledimex followed 3 hours \pm 3 hours later by an intratumoral injection of Ad-RTS-hIL-12. The veledimex will continue to be given once daily on Days 2 through 7. The safety evaluation will be based on the occurrence of related, treatment refractory Grade 3 and 4 AEs within 21 days following the start of Ad-RTS-hIL-12 immunotherapy. A post-treatment safety assessment visit will be conducted on Day 21.

Immunologic biomarkers of response in blood and tumor will also be explored. Full details of the study design can be found in the protocol.

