5.4. Sample size

A maximum of 40 subjects will be treated. Because this patient population is heterogeneous, it is difficult to define a threshold for a clear null and alternative hypothesis. This sample size will allow us to estimate an overall progression rate at 12 weeks with a maximum 95% exact confidence interval half-width of 0.16. This is based on an exact binomial calculation and is an estimate. However, analysis of progression-free survival will be conducted using Kaplan-Meier methods.

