6.2. Analysis Populations

The following subject populations will be evaluated and used for presentation and analysis of the data:

- The safety population will comprise all subjects who have received either the injection of Ad-RTS-hIL-12 or any doses of veledimex
- The veledimex-treated population will comprise subjects who have received the injection of Ad-RTS-hIL-12 and at least one dose of veledimex
- The veledimex-evaluable population will comprise subjects who have received the injection of Ad-RTS-hIL-12 and all 7 doses of veledimex

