10.1. Progression rate

The proportion failed by 12 weeks is denoted as the progression rate, and is derived based on the sum of progression events, death events, and subjects who discontinue the trial due to an AE.

The progression rate will be summarized by HER2 status group and overall for the evaluable population.

An exact 2-sided 95% confidence interval for the proportion of subjects who failed treatment by 12 weeks will also be presented by visit and overall (based on the best response).

Objective Response Rate Tumor response following the start of Ad-RTS-hIL-12 immunotherapy will be assessed using RECIST v1.1. Overall response at Week 12 is based on the totality of the responses for target and non-target lesions, as shown in the table below:

| Target Lesions | Non-target Lesions | New Lesions | Overall Response |
|-------------------|-----------------------------|-------------|------------------|
| CR | CR | No | CR |
| CR | Non-CR/non-PD | No | PR |
| CR | Not evaluated | No | PR |
| PR | Non-PD or not all evaluated | No | PR |
| SD | Non-PD or not all evaluated | No | SD |
| Not all evaluated | Non-PD | No | NE |
| PD | Any | Yes or No | PD |
| Any | PD | Yes or No | PD |
| Any | Any | Yes | PD |

The ORR is defined as the percentage of subjects who have CR or PR at 12 weeks. The ORR will be summarized by HER2 status group and overall. An exact 2-sided 95% confidence interval will also be presented by HER2 status and overall.

For this calculation, responders are defined as those experiencing a CR or a PR. Non-responders are those either with stable or progressive disease. Those subjects who cannot be assessed will be treated as non-responders for the purposes of deriving the percentage of responders and confidence intervals. In addition, the number of subjects whose baseline tumor status (stable disease or PR) improves to PR or better at 12 weeks following the start of Ad-RTS-hIL-12 immunotherapy with RECIST v1.1 will be listed and summarized by HER2 status and overall.

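### The 12-week progression rate counts AE withdrawals as failures, but its apparent analysis set leaves out subjects who withdraw for an AE before the seventh veledimex dose

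*SAP*

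**What the plan says.** SAP 10.1 defines the progression rate as the proportion failed by 12 weeks, "derived based on the sum of progression events, death events, and subjects who discontinue the trial due to an AE". SAP 5.1.2 gives the same definition. Section 10.1 then sets the population: "The progression rate will be summarized by HER2 status group and overall for the evaluable population".

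SAP 6.2 defines three populations, from widest to narrowest. The safety population takes anyone exposed to the vector injection or to veledimex, in whatever amount. The veledimex-treated population needs both: the injection together with one or more veledimex doses. The narrowest set is the only one with evaluable in its name: "The veledimex-evaluable population will comprise subjects who have received the injection of Ad-RTS-hIL-12 and all 7 doses of veledimex".

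SAP 5.2 has the first veledimex dose and the injection on Day 1, and then: "The veledimex will continue to be given once daily on Days 2 through 7". Whether a subject belongs to the third set is therefore decided during the first week.

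SAP 5.4 plans for at most 40 treated subjects and justifies that number by precision: "This sample size will allow us to estimate an overall progression rate at 12 weeks with a maximum 95% exact confidence interval half-width of 0.16". SAP 6.3 rules out imputation. SAP 9.1.2 tabulates compliance separately for doses held and doses missed, so incomplete dosing is foreseen. SAP 10.4 defines a week-12 PFS rate and names no population for it.

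**The concern.** The failure definition and the analysis set work against each other. Counting AE withdrawals as failures ensures that treatment abandoned for toxicity does not pass as success. Requiring all seven doses removes the subjects whose toxicity cut dosing short. An AE withdrawal can then count only if it comes after the seventh dose.

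The resulting estimate describes subjects selected, after treatment began, for having completed the course. It is also the quantity used to justify the sample size, and that justification assumes all treated subjects are analysed. The SAP plans no second analysis of this rate in a wider set.

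**Working it through.** **Inputs from the SAP.** N = 40 treated at most (5.4); failure definition (10.1); seven-dose set (6.2); exact two-sided 95% interval (10.1); stated maximum half-width 0.16 (5.4).

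**Inputs assumed.** The SAP gives neither of these. k is the number of treated subjects who stop veledimex during Days 1 to 7 and leave the trial for an AE, taken as 2 to 8. r is the failure rate among the remaining 40 − k, taken as about 30% to 70%. No other subject is excluded.

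**1. The plan's own figure.** The Clopper-Pearson limits for x failures in n are the 2.5% point of Beta(x, n − x + 1) and the 97.5% point of Beta(x + 1, n − x). The half-width at n = 40 is largest at x = 20. The limits are 0.338 and 0.662, and (0.662 − 0.338)/2 = 0.162. This reproduces the stated 0.16, with all 40 in the denominator.

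**2. Direction.** With x failures among the 40 − k completers, r = x/(40 − k). The seven-dose set reports r. The SAP's own definition applied to all treated gives (x + k)/40. The difference is

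(x + k)/40 − x/(40 − k) = k(1 − r)/40,

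which is positive whenever r is below 100%. For these subjects the understatement is a matter of arithmetic.

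**3. Size at r = 50%.**

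| k | Seven-dose set | All 40 treated | Understatement | Maximum half-width, seven-dose set |
|---|---|---|---|---|
| 0 | 20/40 = 50.0% | 20/40 = 50.0% | 0 | 0.162 |
| 2 | 19/38 = 50.0% | 21/40 = 52.5% | 2.5 points | 0.166 |
| 4 | 18/36 = 50.0% | 22/40 = 55.0% | 5.0 points | 0.171 |
| 6 | 17/34 = 50.0% | 23/40 = 57.5% | 7.5 points | 0.176 |
| 8 | 16/32 = 50.0% | 24/40 = 60.0% | 10.0 points | 0.181 |

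**4. Range over r.** The smallest gap examined is k = 2 with r near 70%: 27/38 = 71.1% against 29/40 = 72.5%, or 1.4 points. The largest is k = 8 with r near 30%: 10/32 = 31.3% against 18/40 = 45.0%, or 13.8 points.

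**5. Subjects who miss or have a dose held but stay on trial.** They are excluded too, but they are not failures by definition. Suppose 8 such subjects are excluded and the 32 completers fail at 50% (16 failures). If none of the 8 fail, the all-treated rate is 16/40 = 40%. If 4 fail, it is 20/40 = 50%. If all 8 fail, it is 24/40 = 60%. The seven-dose set reports 50% each time, so the bias can go either way.

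**The case against.** **The population name.** Section 10.1 says evaluable, not veledimex-evaluable, and the SAP never equates the two. The SAP also cites protocol sections (12.4.2, 9.2.2.7, Appendix 16.3) that do not exist in the supplied protocol. That protocol describes a randomized multicenter trial, whereas the SAP describes a single-arm, single-center one. Its Efficacy Evaluable Population (at least one dose and one post-screening response evaluation) therefore cannot settle the meaning. This stands: the seven-dose reading is an inference. It is still the only reading the SAP itself supports, and if another set was meant, 10.1 needs to name it.

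**Other analyses keep these subjects in view.** ORR and DCR name no restricted population and count subjects who cannot be assessed as non-responders. On that wording, an early AE withdrawal without scans counts against the DCR. Discontinuation reasons are tabulated, and AEs leading to discontinuation are listed. This stands and limits the damage to the progression rate. It also shows that the SAP handles incomplete follow-up conservatively elsewhere, so the progression rate is out of line.

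**Weight.** The primary endpoint is safety. The progression rate is a secondary endpoint in an estimation design without hypotheses, so no alpha, power or decision rule changes. This stands.

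**Stronger readings that do not hold.** A reader might infer that every subject who stops veledimex early pulls the reported rate down. The definition requires leaving the trial for an AE; someone who stops dosing but stays for the week 6 and week 12 scans is not an AE failure, and step 5 shows the effect is then of unknown direction. A reader might also see a conflict with SAP 6.1, under which no subject is removed from a population because of a protocol deviation. Not meeting an exposure-based definition is not removal for a deviation, and the SAP does not classify held doses as deviations.

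**Conclusion.** The point holds in a limited form. If the evaluable population in 10.1 is the veledimex-evaluable population of 6.2, subjects who stop during Days 1 to 7 and leave the trial for an AE are failures under the SAP's definition but are omitted from its estimate. For them the understatement is certain and equals k(1 − r)/40. AE withdrawals after the seventh dose are counted correctly. For subjects with an incomplete course who stay on trial, the exclusion is unnecessary but its bias has no known sign.

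The size cannot be fixed from the documents. Over the assumed range of 2 to 8 such withdrawals among 40, with completer failure rates of about 30% to 70%, it is about 1 to 14 percentage points. The loss of precision is modest: from 0.162 to 0.171 with 36 analysed, or 0.181 with 32. This should be corrected before analysis, but it does not threaten the trial's primary safety objective.

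**What to change.** In SAP 10.1, replace the reference to the evaluable population with an all-treated set from 6.2, using its exact name. The safety population is the better fit: veledimex is given before the injection on Day 1, so a subject who leaves for an AE between the two is in the safety population but not in the veledimex-treated population. The veledimex-treated population is the minimum acceptable choice. Name the same set for the week-12 PFS rate in 10.4, so that the two 12-week measures share a denominator. Keep the seven-dose set as a supportive analysis, labelled as conditional on completing the course.

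The cost is SAP wording and table designations, with no new data. The reported progression rate may be slightly less favourable. In return, the denominator matches the failure definition and the precision statement in 5.4 applies to the set actually analysed.

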5.2. Overall Study Design

This is a single-arm, single-center Phase Ib/II study to examine the safety, tolerability, and preliminary efficacy of providing one cycle of Ad-RTS-hIL-12 immunotherapy following achievement of stable disease or PR on standard first-, second-, or third-line chemotherapy in breast cancer subjects. The subject population includes subjects with locally advanced or metastatic breast cancer of all subtypes. The safety of this therapy and the preliminary evidence of efficacy will guide further studies. Subjects are required to be in stable disease or PR after completion of a minimum of 12 weeks on standard chemotherapy. Subjects who have progressive disease (PD) or a CR after standard chemotherapy are not eligible for the study. Following entry into the trial, subjects will go on a treatment holiday from the standard chemotherapy and enter an immunotherapy phase of treatment.

Scans will be conducted 6 and 12 weeks after the start of Ad-RTS-hIL-12 immunotherapy for determination of tumor response. Radiographic PD at Week 6 must be confirmed at least 4 weeks later, either at Week 12 or earlier if clinically necessitated. In cases of slow tumor growth, the investigator may wait until confirmation of PD at 12 weeks to resume chemotherapy. In cases of unequivocal progression, the investigator may resume chemotherapy prior to 12 weeks and the subject will be considered as treatment failure at 12 weeks.

Upon completion of Week 12, subjects who are considered to have stable disease or better will enter long-term follow-up for up to an additional 36 weeks. In the long-term follow-up period, scans will be performed at 18, 24, 36, and 48 weeks until a radiographic response of PD is confirmed.

The assessment of response will be based on Response Evaluation Criteria in Solid Tumors (RECIST) v1.1 using tumor measurements from contrast-enhanced computed tomography (CT). Tumor response will also be assessed by Immune-Related Response Criteria (irRC) ([Wolchok et al, 2009](#)). Eligible subjects will also be asked to consent to allow ZIOPHARM to obtain scans and tumor measurements taken both a) prior to initiating the prestudy standard chemotherapy and b) after a minimum of 12 weeks of prestudy standard chemotherapy, and not more than 4 weeks prior to study enrollment, in order to confirm their stable disease or PR study entry status.

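### SAP 10.1 defines week-12 failure by events but takes its overall 95% interval from best response, so estimate and interval can describe different quantities

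*SAP*

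**What the plan says.** **The event definition.** SAP 10.1 says that the progression rate "is derived based on the sum of progression events, death events, and subjects who discontinue the trial due to an AE". SAP 5.1.2 gives the same definition.

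**The interval.** Still in 10.1, the SAP promises "An exact 2-sided 95% confidence interval for the proportion of subjects who failed treatment by 12 weeks", which "will also be presented by visit and overall (based on the best response". The parenthesis follows the word overall. The SAP does not say what best response means for this endpoint.

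**The assessment times.** SAP 5.2: "Scans will be conducted 6 and 12 weeks after the start of Ad-RTS-hIL-12 immunotherapy". There are thus two scheduled assessments up to week 12.

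**The analysis set.** SAP 10.1: "The progression rate will be summarized by HER2 status group and overall for the evaluable population". In SAP 6.2 the only set with evaluable in its name is the veledimex-evaluable population: "subjects who have received the injection of Ad-RTS-hIL-12 and all 7 doses of veledimex". The veledimex-treated population, defined beside it, needs the injection and at least one dose.

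**The concern.** Failure by week 12 is cumulative: once a subject has progressed, died or left for an AE, an earlier good scan cannot undo it. Best response works the other way, because it keeps the most favourable assessment. A subject with stable disease at week 6 and progression at week 12 has failed by week 12 but has a best response of stable disease. The same holds for a subject stable at week 6 who then dies or leaves for an AE. Such subjects are plausible, since entry requires stable disease or partial response on prior chemotherapy (SAP 5.2), but the documents do not say how many to expect.

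The denominator raises a second problem. Leaving the trial for an AE is a defined failure. Yet a subject who stops veledimex early for toxicity and leaves has not taken 7 doses, so is not in the set where the rate is calculated.

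The week-12 progression rate is the first secondary objective in SAP section 4 and the quantity behind the precision statement in SAP 5.4. No hypothesis is tested, so the estimate and its interval are the whole result for this endpoint.

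**Working it through.** **1. The plan's own figure.** Inputs from SAP 5.4: "A maximum of 40 subjects will be treated", and a maximum exact 95% half-width of 0.16. The Clopper-Pearson limits for x failures of n are

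- lower = 0.025 quantile of Beta(x, n − x + 1)
- upper = 0.975 quantile of Beta(x + 1, n − x)

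For n = 40 the widest interval is at x = 20: 0.338 to 0.662. The half-width is (0.662 − 0.338)/2 = 0.162, which rounds to 0.16. The planned precision reproduces.

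**2. The two counts.** Let F be the failures by week 12 under the event definition. Let k be those among them who were stable or better at week 6.

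- Point estimate: F/n.
- Proportion behind a best-response interval: (F − k)/n.
- Difference: k/n, or 1/40 = 2.5 points per subject at n = 40. It is larger in the evaluable set or a HER2 group if these have fewer than 40 subjects.

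On the usual meaning of best response, a best response of progression is itself a failure, so the discrepancy runs only one way.

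**3. Size.** The documents give neither F nor k; both are assumptions. With n = 40 and F = 20 the estimate is 50.0% throughout, and its matching interval is 33.8% to 66.2%.

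| k | Best-response count | Proportion | Exact 95% interval | Contains 50%? |
|---|---|---|---|---|
| 0 | 20/40 | 50.0% | 33.8% to 66.2% | yes |
| 2 | 18/40 | 45.0% | 29.3% to 61.5% | yes |
| 4 | 16/40 | 40.0% | 24.9% to 56.7% | yes |
| 8 | 12/40 | 30.0% | 16.6% to 46.5% | no |
| 12 | 8/40 | 20.0% | 9.1% to 35.6% | no |

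The same pattern holds for F = 12, 16, 24 and 28: the best-response interval contains the event rate at k = 2 and 4 and excludes it at k = 8 and 12.

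**4. The denominator.** Suppose that m of n treated subjects did not take all 7 doses and that e of these m failed. The rate moves from F/n to (F − e)/(n − m). It falls if e/m is above F/n and rises if e/m is below it. With assumed values n = 40, F = 20 and m = 4:

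- e = 4: 16/36 = 44.4%
- e = 2: 18/36 = 50.0%
- e = 0: 20/36 = 55.6%

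Subjects who leave for toxicity are all failures and push the rate down when removed. Subjects who merely missed a dose and did not fail push it up. SAP 9.1.2 tabulates held and missed doses separately, so both kinds are foreseen.

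**The case against.** A reader might infer that the SAP scores the stable-then-progressed subject as not failed and so understates the failure rate. The documents do not support that. The rate is defined by events in 5.1.2 and 10.1, and under that definition this subject is a failure. Best response is attached only to the overall interval, and deleting the parenthesis changes no point estimate. The sentence also promises intervals by visit, and the week-12 one would naturally count a week-12 progression.

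The effect is also conditional. Best response is undefined here, and k may be zero. The SAP refers to its own protocol for response details, but the Protocol supplied describes another design (randomised, two arms, 16-week PFS rate) and cannot settle the wording. The text is disturbed at this point, with the words Objective Response Rate running straight into the next sentence, so the parenthesis may be a stray phrase and not a deliberate choice.

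Related results are unaffected by the phrase. SAP 10.4 gives a week-12 PFS proportion with its own exact interval, SAP 10.2 bases DCR on status at 12 weeks, and SAP 5.4 adds Kaplan-Meier analysis of PFS. The primary endpoint is safety, and no decision rule depends on this interval.

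All of this limits the point. It does not remove the conflict: as written, one section gives a proportion and its overall interval different bases, and on the usual reading of best response the interval's basis is wrong for a cumulative failure proportion.

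**Conclusion.** The point holds for the overall interval, not for the rate. On the usual meaning of best response, that interval is built on a proportion too low by 1/n for each subject stable at week 6 who progresses, dies or leaves for an AE by week 12. At n = 40 that is 2.5 points per subject. With the assumed 20 failures, 8 such subjects are enough for the interval to exclude its own estimate; with none, there is no effect.

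The population point holds in part. The set used for the rate leaves out a kind of failure that the definition names. A reader might infer that this too must lower the reported rate. The documents do not establish that, because the net effect depends on who else missed doses and whether they failed. It also rests on reading the evaluable population in 10.1 as the veledimex-evaluable population in 6.2, the only candidate defined.

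**What to change.** In SAP 10.1, delete the parenthesis about best response. State that the exact 95% interval uses the same numerator and denominator as the point estimate: subjects with progression, death or AE discontinuation up to and including week 12, over the population named for the rate.

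Name that population explicitly. The veledimex-treated population, already defined in 6.2, keeps a subject who had the injection and at least one dose and then left for toxicity in the analysis, as a failure. Report the rate in the veledimex-evaluable (7-dose) population as a sensitivity analysis.

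The cost is SAP wording only, with no new data or assessments. The reported interval may be somewhat less favourable, and the rate may move in either direction with the change of population.
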